7.5.1.2 Plasma Nicotine and Cotinine

Nicotine and cotinine concentrations will be measured in plasma to evaluate the exposure to nicotine in all three study arms. No sampling for PK profile will be done for subjects in the SA arm (Day 5 to Day 6) and only one blood sampling will be done on each of Day 5 and Day 6.

- On Day 0 to Day 4 (all study arms):

One blood sample per day will be taken in the evening between 08:00 PM and 09:30 PM.

- Nicotine/Cotinine Pharmacokinetic (PK) Profile on Day 5 and Day 6 (THS 2.2 Menthol and mCC arms only):

In total, 9 blood samples will be drawn on Day 5. The first blood sample on Day 5 will be drawn within 15 minutes prior to the first product use. On Day 5, the start time of the first product use (T_0) will serve as reference for the time to peak concentration. An additional 8 blood samples will be drawn in 2 hour intervals after the start of product use. The last blood sample should be drawn no later than 11:00 PM, corresponding to the end of product use. At all time points, if the subject wants to use the product around the time of

the blood draw, he/she should use it first and the blood will be drawn after product use. Depending on the time of the first product use, it may be that fewer than 8 blood samples will be collected from a subject after T_0 .

On Day 6, two blood samples will be drawn. The first one will be 20 hours after T_0 and the second blood sample will be 24 hours after T_0 (with T_0 being the start time of first product use at Day 5).

- On Day 5 and Day 6 (SA arm only):

On Day 5, one blood sample will be drawn in the evening between 08:00 PM and 09:30 PM.

On Day 6, one blood sample will be drawn between 08:00 AM-09:30 AM.

- On Day 30 Visit (Day 30), Day 60 Visit (Day 60), Day 90 Visit (Day 90) (all study arms):

One blood sample will be drawn during these visits, irrespective of the time of product use.

7.5.1.3 *Other Biomarkers of Exposure*

BoExp will be measured as per the Schedule of Events (Appendix 1):

- In 24-hour urine collection samples during both confinement and ambulatory periods from Day 0 onwards to Day 5 and on Day 30 Visit, on Day 60 Visit , and on Day 90 Visit.
- In 4-hour urine fraction during both confinement and ambulatory periods collected on Day -1, and Day 90 Visit (Day 91).

The following BoExp will be measured:

- Selected primary BoExp: MHBMA, 3-HPMA, S-PMA, and Total NNAL.

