
Version	Date of Revision	Revision
		
imputation. Clarified that the sensitivity analysis on the compliant population will be produced also for the comparison between THS 2.2 Menthol and SA.
 

○ In Section 12.6.2 and 12.6.2.5:

○ Added summaries for the endpoints of the primary analysis

○ Clarified that the p-value will only be produced at Day 90 conditionally on the statistical significance at Day 5

○ Clarified that the CO breath test will be analyzed in the regular scale

○ Text and list of TFL adjusted according to the general rules for summaries of BoExp

○ Summaries of Nicotine and cotinine concentration not produced as a change from baseline and data will be analyzed on the log space. The mixed model code was removed to analyze results using ANCOVA by timepoint for consistency with other analyses.

○ Clarified that the ratio will be estimated for the analysis of nicotine and cotinine <math>C_{peak}</math> and <math>C_{avg}</math> on Day 5. The median difference will be tabulated for the <math>t_{peak}</math> on Day 5.

○ CYP1A2 and CYP2A6 activity will be analyzed in the log space and the THS 2.2 Menthol:mCC ratio will be presented.

○ Percent change from Baseline will be summarized and listed for the QSU-brief. Data will be analyzed using the same model adopted for the analysis of nicotine and cotinine over study days, amended as appropriate to obtain the required comparison. Only Total score data will be plotted.

○ Summaries and listing of percent change from Baseline added for mCEQ, MNWS, and Ames mutagenicity. Clarified that for the MNWS the results will be presented for the day prior to the assessment.

○ Section of HST questionnaire data moved within the questionnaires Section 7.3.6.

○ Risk markers analyzed for the FAS and PP set. Blood pressure, HbA1c, LDL, HDL, TG, TC, WBC, body weight and waist circumference will be analyzed in the regular scale. 8-epi-PGF2a, 11 DTX-B2, sICAM will be analyzed in the logarithmic scale. Other risk markers will be logarithmically transformed prior to analysis if there is evidence of non-normality by means of Shapiro-Wilks test.

○ In Section 12.6.4:

Philip Morris Products S.A.

Protocol ZRHM-REXA-08-US

Statistical Analysis Plan

Final v 3.0 / 29 May 2015

Confidential

Page 11 of 122

Version	Date of Revision	Revision

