## 7.2 Pharmacokinetic Parameters

The peak nicotine and cotinine plasma concentration ( $C_{peak}$ ) and time to peak concentration ( $t_{peak}$ ) will be obtained directly from the concentrations taken on Day 5. If the peak concentration occurs at more than one time point then  $t_{peak}$  will be assigned to the first value. The weighted average concentration over 24 hours on Day 5 ( $C_{avg}$ ) will be calculated by dividing the area under the curve from 0 to 24 h ( $AUC_{0-24\ h}$ ) by 24, where the  $AUC_{0-24\ h}$  is calculated using the linear trapezoidal rule.

Since the samples are taken whilst the subjects are smoking freely all samples must be non-missing for the parameters to be calculated as  $C_{peak}$  (and  $t_{peak}$ ) could occur at any time.

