### 12.6.2.3 Nicotine and Cotinine Pharmacokinetic Parameters

The parameters  $C_{peak}$ ,  $C_{avg}$  and  $t_{peak}$  will be calculated on Day 5 as described in Section 7.2 “**Pharmacokinetic Parameters**”. The data will be listed and summarized for both nicotine and cotinine.

The analysis will compare the log-transformed  $C_{peak}$  and  $C_{avg}$  on Day 5 between the THS 2.2 Menthol and mCC arms. An analysis of variance (ANOVA) model will be used with terms for sex, average daily mCC consumption over the last 4 weeks as reported during screening and randomization arm.

The SAS code will be similar to that described in Section 12.6.1.3 “**Sensitivity Analysis**”, with no baseline value being included in the model.

LS means for each product along with the ratio (THS 2.2 Menthol : mCC) and 95% CI will be presented in the tables.

For  $t_{peak}$  on Day 5 the comparison between the THS 2.2 Menthol and mCC arms will be made by the Wilcoxon Rank Sum test using PROC NPAR1WAY in SAS. Median difference and 95% CI using the Hodges-Lehmann estimate will be tabulated.

The following code will be used:

```
Proc npar1way data=_data_ hl median;
Class randomization_arm;
Var tpeak;
Run;
```

All summaries and analyses will be performed on the PP Set and FAS.

The data will be presented in the below outputs:

TFL number	Title
TABLES	
15.2.4.21.1	Descriptive Statistics of Plasma Nicotine and Cotinine PK Parameters on Day 5 – PP Set
15.2.4.21.2	Descriptive Statistics of Plasma Nicotine and Cotinine PK Parameters on Day 5 – FAS
15.2.4.22.1	Analysis of Plasma Nicotine and Cotinine PK Parameters on Day 5 – PP Set
15.2.4.22.2	Analysis of Plasma Nicotine and Cotinine PK Parameters on Day 5 – FAS
LISTINGS	
15.3.3.4	Listing of Plasma Nicotine and Cotinine Pharmacokinetic Parameters on Day 5

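### The SAP plans a Wilcoxon rank-sum test for Day 5 time to peak, but the code it prints asks for the median-score test and omits the Wilcoxon option

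*SAP*

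**What the plan says.** SAP 12.6.2.3 says of the Day 5 analysis of tpeak that the two arms' comparison "will be made by the Wilcoxon Rank Sum test using PROC NPAR1WAY in SAS". On output it says: "Median difference and 95% CI using the Hodges-Lehmann estimate will be tabulated". The next sentence is "The following code will be used", followed by a four-line program whose PROC statement reads "Proc npar1way data=_data_ hl median". The class variable is the randomization arm and the analysis variable is tpeak.

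The analysis is to be run for nicotine and for cotinine, on the PP Set and on the FAS. Time to peak is a listed endpoint under a secondary objective to describe the PK profiles (SAP 5.2). The revision history in SAP 3.1 has an entry that begins "The median difference will be tabulated for the" and refers to tpeak. It records a change but does not reconcile the text of 12.6.2.3 with its code.

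**The concern.** The text names one test and the code requests another. In PROC NPAR1WAY the rank-sum test is requested by WILCOXON, the median-score (Brown-Mood) test by MEDIAN, and the Hodges-Lehmann shift by HL. Naming one score option replaces the default set of analyses that would otherwise include Wilcoxon. That is knowledge of the software and is not stated in either document. The absence of the WILCOXON keyword can be seen in the SAP itself.

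The wording makes the code binding. For Cpeak and Cavg in the same section, and for CYP1A2 in 12.6.2.4, the SAP says only that the code will be similar to code given elsewhere. For tpeak it prints the code and says it will be used.

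At stake is any p-value or statement of significance for tpeak. It could come from a test the text does not name, in four comparisons (two analytes by two analysis sets).

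**Working it through.** **Text against code.**

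| Element | Text of SAP 12.6.2.3 | Printed code | Agree? |
|---|---|---|---|
| Estimate and 95% CI | Hodges-Lehmann | HL | yes |
| Test | Wilcoxon rank-sum | MEDIAN, no WILCOXON | no |

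A likely explanation is that MEDIAN was added to obtain the median difference mentioned in the revision history. HL already supplies that.

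**Is there a figure to reproduce?** No. Neither document gives a power, sample size or expected distribution for tpeak, so the size of the effect rests on assumptions.

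**Inputs from the documents.** Allocation is 80 THS 2.2 Menthol to 40 mCC (SAP 8). Tests other than the primary ones are two-sided at 5% (Protocol 12.1.5). On sampling, Protocol 7.5.1.2 says: "An additional 8 blood samples will be drawn in 2 hour intervals after the start of product use". The PK profile is taken in the THS 2.2 Menthol and mCC arms only, so the comparison is two-sample.

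**Assumed inputs.** Centre 10 h, SD 4 h and shift 2 h, with normal, logistic, uniform and Laplace shapes. Times are either continuous or rounded to a 2-hour grid from 0 to 16 h.

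**Asymptotic relative efficiency** of the median test to Wilcoxon is f(m)² / [3(∫f²)²], where f is the density and m its median:

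- normal: (2/π)/(3/π) = 0.667
- logistic: (1/16)/(3/36) = 0.75
- uniform: 1/3 = 0.33
- Laplace: (1/4)/(3/16) = 1.33

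**Simulated power.** There were 6,000 trials per setting. Both are linear rank tests, z = (S − n₁ā)/√v, where S is the sum of the scores aᵢ in the first arm, ā their overall mean, and v = n₁n₂/[N(N−1)] · Σ(aᵢ − ā)². For Wilcoxon the scores are midranks. For the median test the score is 1 if the rank exceeds (N+1)/2 and 0 otherwise, averaged over ties.

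| Shape | Continuous: Wilcoxon vs median | 2-hour grid: Wilcoxon vs median |
|---|---|---|
| Normal | 71% vs 47% | 69% vs 57% |
| Logistic | 75% vs 56% | 75% vs 67% |
| Uniform | 68% vs 27% | 60% vs 34% |
| Laplace | 85% vs 81% | 83% vs 87% |

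On the grid, the differences (Wilcoxon minus median) are 69 − 57 = 12, 75 − 67 = 8, 60 − 34 = 26 and 83 − 87 = −4 points.

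**Range over the other assumptions.** With SD from 2 to 6 h and shift from 1 to 2 h on the grid, the median test loses about 1 to 13 points for normal data. For Laplace data it is equal or up to about 5 points better.

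**How often the two tests reach different decisions.** With the 2 h shift they disagreed on significance in about 8% to 42% of simulated trials, depending on shape and grid. With no shift they disagreed in about 3% to 4%.

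**The case against.** The strongest reply is that little of what will be reported depends on the keyword. The SAP commits to tabulating the Hodges-Lehmann difference and its interval, and HL is in the code. Where the SAP wants a p-value in a table it says so, as in 12.6.1.1 for the primary endpoints. It has no such line for tpeak. The prose makes the intended test clear, and a programmer or quality-control check may well notice the difference. The endpoint is descriptive, has no part in the success criterion (SAP 5.5.2), and secondary endpoints carry no multiplicity adjustment (SAP 12.1.7). All of this stands, and it makes the point minor. It does not remove it: a comparison that "will be made by the Wilcoxon Rank Sum test using PROC NPAR1WAY in SAS" implies a test result, and the printed program would not produce that result.

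Three stronger readings are tempting, and the documents do not support them.

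- A reader might infer that the interval is wrong too. It is not, because text and code agree on Hodges-Lehmann.
- A reader might infer that the printed test is simply weaker. That holds for the normal, logistic and uniform shapes tried, but not for Laplace data on the grid, and the documents do not say which shape applies.
- A reader might infer that ties from two-hourly sampling make the loss worse. In the simulation the grid narrows the gap for the normal, logistic and uniform shapes and reverses it for Laplace. The number of ties is also uncertain, because tpeak is defined by actual time (SAP 5.2).

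**Conclusion.** Wrong as written, and minor. SAP 12.6.2.3 names the Wilcoxon rank-sum test, but its binding code requests a median-score test in its place. Any p-value or significance statement for Day 5 tpeak could therefore come from a test other than the one stated. The Hodges-Lehmann difference and 95% CI do not change, and neither do the primary conclusions.

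On the 2-hour grid, under the main assumptions, the effect on power runs from a loss of about 26 points (uniform) to a gain of about 4 (Laplace). These figures rest on assumed SD, shift and shape, and on the full 80:40. The number analysed may be smaller: SAP 7.2 requires every sample to be present before a PK parameter is calculated, and Protocol 7.5.1.2 expects that some subjects may give fewer than eight samples after first use. The conclusion that text and code disagree needs none of these assumptions. It needs only the meaning of the SAS options.

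**What to change.** Change the PROC statement to `Proc npar1way data=_data_ wilcoxon hl;` so that code and text agree. This replaces one option and leaves the tabulated estimate and interval as they are.

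Optionally, add a sentence stating that the Hodges-Lehmann shift is THS 2.2 Menthol minus mCC, and set the reference class in the HL option to match. The section gives a direction for Cpeak and Cavg but none for tpeak, and the replacement line above does not set one by itself. It would also help to say whether a tpeak p-value will be tabulated.

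The cost is one word of code and, if the options are taken up, a sentence or two of text. No data collection, sample size or primary analysis is affected.

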#### 12.6.2.4 CYP1A2 Activity

CYP1A2 activity will be measured in plasma on Day 0, Day 5 and Day 90. In this study the CYP1A2 activity will be calculated using the molar ratio of PX and CAF, as described in Section 7.1.3 “CYP1A2”. Descriptive statistics of the values and percent change on Days 5 and 90 from Day 0 and supportive listings will be provided.

The analysis will compare the log-transformed Day 5 values between the THS 2.2 Menthol and mCC arms and between the THS 2.2 Menthol and SA arms. ANCOVA models will be used on CYP1A2 activity levels with terms for log-transformed baseline, sex, average daily mCC consumption over the last 4 weeks as reported during screening and randomization arm. No adjustment will be made for multiple comparisons. If the results from the Day 5 analysis are significant (one-sided p-value <0.025) then the statistical significance will be repeated for the analysis at the Day 90 values. The SAS code will be similar to that described in Section 12.6.1.3 “Sensitivity Analysis”.

Geometric LS means for each product along with the ratio (THS 2.2 Menthol :mCC) and 95% CI will be presented in the tables.

CYP1A2 activity will also be examined to compare the observed reductions in THS 2.2 Menthol vs. SA using the same methodology as above.

If there are any CYP1A2 assessments performed within 5 half-lives since the use of a concomitant medication affecting CYP1A2 activity, the analysis will be repeated by excluding these assessments for both the PP Set and FAS

All summaries and analyses will be performed on the FAS and PP Set.

The data will be presented in the below outputs:

TFL number	Title
TABLES	
15.2.4.23.1	Descriptive Statistics of CYP1A2 Activity (%) – PP Set
15.2.4.23.1.1	Descriptive Statistics of CYP1A2 Activity (%) Excluding Assessments within 5 Half-Lives of a Concomitant Medication Affecting CYP1A2 Activity – PP Set
15.2.4.23.2	Descriptive Statistics of CYP1A2 Activity (%) – FAS
15.2.4.23.2.1	Descriptive Statistics of CYP1A2 Activity (%) Excluding Assessments within 5 Half-Lives of a Concomitant Medication Affecting CYP1A2 Activity – FAS
15.2.4.24.1	Analysis of CYP1A2 Activity (%) – PP Set
15.2.4.24.1.1	Analysis of CYP1A2 Activity (%) Excluding Assessments within 5 Half-Lives of a Concomitant Medication Affecting CYP1A2 Activity – PP Set
15.2.4.24.2	Analysis of CYP1A2 Activity (%) – FAS
15.2.4.24.2.1	Analysis of CYP1A2 Activity (%) Excluding Assessments within 5 Half-Lives of a Concomitant Medication Affecting CYP1A2 Activity – FAS
LISTINGS	
15.3.4.1	Listing of CYP1A2 Activity and Changes from Baseline

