9. Any subject with an history of adverse events linked to caffeine or caffeine containing drugs (e.g., Vivarin), such as but not limited to hypersensitivity or allergy.	Safety	X	X
10. The subject has used nicotine-containing products other than commercially available mCC (either tobacco-based products or NRT), as well as electronic cigarettes and similar devices, within 4 weeks prior to assessment.	Effect	X	X
11. The subject has received medication (prescription or over-the-counter) within 14 days or within five half-lives of the drug (whichever is longer) prior to the Admission Day (Day -2), which has an impact on CYP1A2 or CYP2A6 activity.	Effect		X

Exclusion Criteria	Rationale	Screening	Day of Admission (Day -2)
12. If a subject has received any medication (prescribed or over-the-counter) within 14 days prior to Screening or prior to the Admission Day (Day -2), it will be decided at the discretion of the Investigator if these can potentially interfere with the study objectives or subject's safety.	Effect	X	X
13. Concomitant use of nonsteroidal anti-inflammatory drugs (NSAIDs) or acetylsalicylic acid.	Effect	X	X
14. The subject has a positive alcohol test and/or the subject has a history of alcohol abuse that could interfere with the subject's participation in the study.	Administrative	X	X
15. The subject has a positive urine drug test.	Administrative	X	X
16. Positive serology test for human immunodeficiency virus (HIV)1/2, hepatitis B or hepatitis C.	Safety	X	
17. Donation or receipt of whole blood or blood products within 3 months prior to Admission.	Safety	X	X
18. The subject is a current or former employee of the tobacco industry or of their first-degree relatives (parent, sibling, child).	Administrative	X	
19. The subject is an employee of the investigational site or any other parties involved in the study or of their first-degree relatives (parent, sibling, and child).	Administrative	X	
20. The subject has participated in a clinical study within 3 months prior to the Screening Visit.	Safety	X	

Data and information contained in this document are considered to constitute trade secrets and confidential commercial information, and the legal protections provided to such trade secrets and confidential information are hereby claimed under the provisions of United States law. No part of this document may be publicly disclosed without the written consent of Philip Morris International.

Exclusion Criteria	Rationale	Screening	Day of Admission (Day -2)

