6.7 Concomitant Medication

No medication should be taken during the study from the screening to the EOS (time of discharge from Day 90 Visit (Day 91) plus 28 days safety follow-up period) without prior informing the Investigator. However, the Investigator is responsible for the medical care of the subjects during their participation in this study. Any decisions regarding the prescribing of medication will be made in the best interests of the subject.

Data and information contained in this document are considered to constitute trade secrets and confidential commercial information, and the legal protections provided to such trade secrets and confidential information are hereby claimed under the provisions of United States law. No part of this document may be publicly disclosed without the written consent of Philip Morris International.

In the SA arm, subjects may be provided with NRT if considered necessary by the Investigator or requested by the subject. The use of medication supportive for smoking abstinence other than NRT will not be allowed.

Concomitant use of NSAIDs and acetylsalicylic acid (including over-the-counter products) is not allowed, as all of them could interfere with risk markers such as 11-DTX-B2. Acetaminophen will be allowed at a daily total dose of up to 3000 mg. Any medication (except medication containing estrogen) with an impact on the CYP1A2 and CYP2A6 metabolism (as prescription and over-the-counter products) as shown in Table 3 must be avoided.

If the use of a concomitant medication cannot be avoided for the subject's safety, it must be fully documented in the Source Document and transcribed into the eCRF (for details, see Section 7.4.7).

The drugs and substances shown in Table 3 are a selection of drugs considered to have an impact on CYP1A2 and/or CYP2A6 activity (Chang et al., 1999, Ingelman-Sundberg et al., 1999, Lacy et al., 2007). Prior to database close, concomitant medication will be assessed according to their potential impact on CYP1A2 and CYP2A6 activity and potential impact on the study results.

Concomitant medication will first be assessed at the Screening Visit. To be eligible for the study, any medication with impact on CYP1A2 and CYP2A6 metabolism must be discontinued at least 2 weeks prior to Admission to the clinic or for at least 5 half-lives (whichever is longer). They must not be used during the entire study until the Day 91 (completion of the study).

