### 12.6.2.5 Risk Markers

The risk markers are:

- Systolic and diastolic blood pressure on Day 0, Day 6, Day 30 Visit, Day 60 Visit, and Day 90 Visit.
- hs-CRP, homocysteine, blood glucose, LDL, HDL, TG, and TC in serum on Day 0, Day 30 Visit, Day 60 Visit, and Day 90 Visit.
- Fibrinogen in plasma on Day 0, Day 30 Visit, Day 60 Visit, and Day 90 Visit.
- HbA1c in blood on Day 0 and Day 90 Visit.
- sICAM-1 in serum on Day 0, Day 6, Day 30 Visit, Day 60 Visit, and Day 90 Visit.
- WBC and platelet count in blood on Day 0, Day 6, Day 30 Visit, Day 60 Visit, and Day 90 Visit.
- 8-epi-PGF2 $\alpha$  and 11-DTX-B2 in 24 hour urine on Day 0, Day 5, Day 30 Visit, Day 60 Visit, and Day 90 Visit (expressed as concentration adjusted for creatinine).

- Body weight and waist circumference on Day -2 and Day 90 Visit.

The results along with the changes from baseline will be listed and summarized. In addition line graphs will be produced for product means (and 95% CI) over all timepoints.

The analysis will compare the results on Day 90 between the THS 2.2 Menthol and mCC arms, and between the THS 2.2 Menthol and SA arms for the FAS and PP set. An ANCOVA model will be used with terms for Baseline, sex, average daily mCC consumption over the last 4 weeks as reported during screening and randomization arm. No adjustment will be made for multiple comparisons.

Blood pressure, HbA1c, LDL, HDL, TG, TC, WBC, body weight and waist circumference will be analyzed in the regular scale. 8-epi-PGF2 $\alpha$ , 11-DTX-B2, sICAM will be analyzed in the logarithmic scale. Other risk markers will be logarithmically transformed prior to analysis if there is evidence of non-normality by means of Shapiro-Wilks test.

The SAS code will be the same as described in Section 12.6.1.1 “**Analysis of Biomarkers of Exposure for Primary Endpoints**”.

LS means for each product along with the difference (THS 2.2 Menthol - mCC) or ratio (THS 2.2 Menthol : mCC) and 95% CI will be presented in the tables along with a forest plot of the results.

If there are any 11-DTX-B2 assessments performed within 5 half-lives since the use of a concomitant medication affecting the production of 11-DTX-B2, the analysis will be repeated by excluding these assessments for both the PP Set and FAS

All tables, figures and analyses will be produced for the FAS and PP Set. Figures will be produced for the PP Set.

The data will be presented in the below outputs:

TFL number	Title
FIGURES	

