#### **12.6.3.4 CYP2A6 Activity**

CYP2A6 activity will be measured in plasma on Day 0, Day 6 and Day 91. In this study the CYP2A6 activity will be calculated using the metabolic ratio of trans 3' hydroxycotinine and cotinine, as described in Section 7.1.4 “CYP2A6”. Descriptive statistics of the values and changes on Day 6 and Day 91 from Day 0 and supportive listings will be provided.

The analysis will compare the log-transformed Day 6 values between the THS 2.2 Menthol and mCC arms and between the THS 2.2 Menthol and SA arms. ANCOVA models will be used with terms for log-transformed baseline, sex, average daily mCC consumption over the last 4 weeks as reported during screening and randomization arm. No adjustment will be made for multiple comparisons. If the results from the Day 6 analysis are significant (one-sided p-value < 0.025) then the statistical significance will be repeated for the analysis at the Day 91 values. The SAS code to be used is similar to the model reported in Section 12.6.1.3 "Sensitivity Analysis".

Geometric LS means for each product along with the ratio (THS 2.2 Menthol : mCC) and 95% CI will be presented in the tables

CYP2A6 activity will also be examined to compare the reductions in THS 2.2 Menthol vs. SA using the same methodology as above.

If there are any CYP2A6 assessments performed within 5 half-lives since the use of a concomitant medication affecting CYP2A6 activity, the analysis will be repeated by excluding these assessments for both the PP Set and FAS

All summaries and analyses will be performed on the FAS and PP Set.

The data will be presented in the below outputs:

TFL number	Title
TABLES	
15.2.4.62.1	Descriptive Statistics of CYP2A6 Activity (%) – PP Set
15.2.4.62.1.1	Descriptive Statistics of CYP2A6 Activity (%) Excluding Assessments

TFL number	Title
	within 5 Half-Lives of a Concomitant Medication Affecting CYP2A6 Activity - PP Set
15.2.4.62.2	Descriptive Statistics of CYP2A6 Activity (%) – FAS
15.2.4.62.2.1	Descriptive Statistics of CYP2A6 Activity (%) Excluding Assessments within 5 Half-Lives of a Concomitant Medication Affecting CYP2A6 Activity - FAS
15.2.4.63.1	Analysis of CYP2A6 Activity (%) – PP Set
15.2.4.63.1.1	Analysis of CYP2A6 Activity (%) Excluding Assessments within 5 Half-Lives of a Concomitant Medication Affecting CYP2A6 Activity – PP Set
15.2.4.63.2	Analysis of CYP2A6 Activity (%) – FAS

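### The repeat analyses that check CYP1A2 and CYP2A6 for drug interference use 5 half-lives without the protocol's 14-day minimum, and the same window for 11-DTX-B2 is unsupported

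*SAP*

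**What the plan says.** Three SAP sections define a repeat analysis by the time since an interfering drug was used:

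- 12.6.2.4, CYP1A2 (secondary): assessments "performed within 5 half-lives since the use of a concomitant medication affecting CYP1A2 activity".
- 12.6.3.4, CYP2A6 (exploratory): assessments "performed within 5 half-lives since the use of a concomitant medication affecting CYP2A6 activity".
- 12.6.2.5, 11-DTX-B2 (secondary, as a risk marker): assessments "performed within 5 half-lives since the use of a concomitant medication affecting the production of 11-DTX-B2".

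In each case, if such assessments exist, "the analysis will be repeated by excluding these assessments for both the PP Set and FAS". The main analysis on the same populations keeps them. No section gives a minimum number of days or says which medications count.

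The protocol has a timing rule for the CYP drugs. Exclusion criterion 11 rules out a subject who received a drug affecting CYP1A2 or CYP2A6 "within 14 days or within five half-lives of the drug (whichever is longer) prior to the Admission Day (Day -2". Section 6.7 repeats it: such drugs "must be discontinued at least 2 weeks prior to Admission to the clinic or for at least 5 half-lives (whichever is longer".

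For 11-DTX-B2 the protocol has a ban and no timing rule. Exclusion criterion 13 reads "Concomitant use of nonsteroidal anti-inflammatory drugs (NSAIDs) or acetylsalicylic acid". Section 6.7 says that concomitant use of these drugs "is not allowed, as all of them could interfere with risk markers such as 11-DTX-B2".

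**The concern.** The repeat analyses are the SAP's planned check on whether the CYP1A2, CYP2A6 and 11-DTX-B2 results depend on medication. The PP Set does not do this job: SAP Table 22 classes the use of drugs known to affect CYP2A6 or CYP1A2 as a minor deviation, and only major deviations that affect evaluability remove a subject from the PP Set.

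A floor of 14 days matters only when 5 half-lives is shorter than that. By adding it, the protocol declined to rely on 5 half-lives alone for short-lived drugs. The SAP drops the floor for the same drugs and gives no reason, and SAP Section 9 (changes from the protocol) does not mention it. If an effect on the enzyme outlasts the drug, affected values stay in the repeat analysis, and agreement between the repeat and the main analysis will look more reassuring than it is. The same question arises for 11-DTX-B2, where the protocol offers no window to fall back on.

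**Working it through.** The plan states no figure to reproduce. The check compares two windows.

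**CYP1A2 and CYP2A6.** Inputs: the SAP window is 5 × t½ (12.6.2.4, 12.6.3.4). The protocol window is max(14 d, 5 × t½) (criterion 11, Section 6.7). The documents give no half-lives, so t½ is varied over an assumed range.

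The windows are equal when 5 × t½ = 14 d, so t½ = 14/5 = 2.8 d = 67.2 h.

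| Assumed t½ | SAP window (5 × t½) | Protocol window | Gap |
|---|---|---|---|
| 4 h | 0.83 d | 14 d | 13.2 d |
| 12 h | 2.5 d | 14 d | 11.5 d |
| 24 h | 5 d | 14 d | 9 d |
| 48 h | 10 d | 14 d | 4 d |
| 67.2 h | 14 d | 14 d | 0 |
| 96 h | 20 d | 20 d | 0 |

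After 5 half-lives, 0.5^5 = 3.1% of the drug remains. The SAP window therefore covers clearance of the drug, but not an effect that persists after clearance.

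The window matters for short courses that end before the assessment. A drug still being taken at the time of sampling, such as a permitted estrogen, falls inside either window.

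**A case where the window decides.** Protocol Table 3 lists lidocaine. Section 7.7.3.2 and Appendix 7 offer it on request at the nasal collection, including on Day 0 in the afternoon or evening. The Day 5 CYP1A2 sample is drawn about 5 days later. With 5 × t½ < 5 d, that is t½ below about 1 day, the SAP keeps the sample; a 14-day window would drop it. The SAP does not say whether nasal lidocaine counts.

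**11-DTX-B2.** The protocol gives no washout, so only a conditional statement is possible. Assume that the effect of acetylsalicylic acid lasts a platelet lifespan of 7 to 10 days; this is not in the documents. Five half-lives is then too short for any t½ below 7/5 = 1.4 d (33.6 h) at the low end, or 10/5 = 2 d (48 h) at the high end. With an assumed t½ of 0.25 to 6 h (acetylsalicylic acid to salicylate), the SAP window is 1.25 to 30 h.

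As a purely hypothetical size, suppose m retained values in an arm of n are lowered by a fraction s = 0.5 to 0.9. The arm's geometric mean then shifts by exp(m × ln(1 − s)/n) − 1:

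- n = 40, m = 1: −1.7% to −5.6%
- n = 40, m = 2: −3.4% to −10.9%
- n = 80, m = 1: −0.9% to −2.8%

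For scale, Protocol 12.2 powers the study for a 20% difference in 11-DTX-B2.

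**The case against.** Criterion 11 and Section 6.7 set an eligibility washout before Day -2; the SAP sets an analysis exclusion for use on study. The protocol nowhere fixes 14 days as an analysis window, so a reader who infers that the SAP contradicts the protocol goes too far. This stands: the two apply different standards to the same drugs, without direct conflict.

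A reader might also take the 14-day rule as the protocol's washout for 11-DTX-B2. It is not; it covers only CYP1A2 and CYP2A6 drugs, and the 11-DTX-B2 part rests on the stated assumption.

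It is tempting to say that affected values will remain in the repeat analyses. The documents do not show this. Table 3 does not label any drug an inducer and gives no half-lives, and nothing states how long an effect lasts after clearance. The protocol's floor hints at persistence for the CYP drugs and does no more.

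There are safeguards. Interfering CYP drugs must not be used until Day 91, NSAIDs and acetylsalicylic acid are banned, unauthorised medication may lead to discontinuation (Protocol 5.1.3), and Section 6.7 requires a review of concomitant medication before database close. These make cases rarer, but do not alter the window that the SAP fixes for those that occur. The table titles disclose the 5-half-life rule, which limits the risk of misreading.

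The longer window also has a price. If nasal lidocaine counts, it could remove Day 5 CYP1A2 and Day 6 CYP2A6 values, the timepoints whose significance decides whether Day 90 and Day 91 are tested. That is a reason to settle the medication list first.

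**Conclusion.** The point holds for CYP1A2 and CYP2A6. The SAP's exclusion window omits the 14-day minimum that the protocol applies to the same drugs at entry, and for any half-life below 67.2 h it is shorter, by up to almost 14 days. For 11-DTX-B2 the point is conditional: if the effect of acetylsalicylic acid outlasts its plasma half-life, a 5-half-life window misses it, and the SAP gives no argument that it does not.

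The consequence is limited. These are conditional repeats on two secondary markers and one exploratory marker, the main analyses keep all assessments, and no primary endpoint is touched. Nothing in the documents shows that any subject falls in the gap, so the geometric-mean shifts are illustrations and not estimates of bias. The change is worth making because the repeats exist only to check for interference, and the present window weakens that check for short-lived drugs.

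**What to change.** - In SAP 12.6.2.4 and 12.6.3.4, define the excluded assessments as those within 14 days or 5 half-lives of the last use of an interfering medication, taking the longer period.
- In SAP 12.6.2.5, apply the same 14-day minimum, at least for acetylsalicylic acid.
- Carry the definition into the matching tables on both populations: CYP1A2 (15.2.4.23.x.1, 15.2.4.24.x.1), CYP2A6 (15.2.4.62.x.1, 15.2.4.63.x.1) and 11-DTX-B2 (15.2.4.25.x.1, 15.2.4.32.x.1).
- Before database lock, list which medications count for each marker. Protocol Table 3 is not exhaustive, so the list should say explicitly whether nasal lidocaine and permitted estrogens are on it. The medication review required by Protocol 6.7 is the natural place for this.

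This is an analysis rule only and changes nothing about which medication subjects may take. The cost is wording in three sections, table titles (which SAP Section 3 allows to change without an amendment) and one date window in programming, with no new data. The downside is that more assessments leave a supportive analysis, possibly including some Day 5 and Day 6 values; the number dropped should be reported beside each repeat.
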